#### Vital Signs, Weight and Karnofsky Performance Status

Descriptive statistics will be used to summarize vital signs, weight, and Karnofsky performance status. For continuous outcomes the mean, standard deviation, median, 25% percentile, 75% percentile, minimum, and maximum will be reported for change from baseline at each scheduled visit. For discrete (i.e., Karnofsky performance status) outcomes, descriptive analyses will be based on the distribution of this outcome and will be reported as percentages and patient counts by category.

#### MDASI-BT

The sample size for this trial was based on the primary end point of the study.

Received MDASI-BT and MDASI-SP forms will be checked versus the timing schedule and considered as valid if they fall within one week of the scheduled assessment. Compliance rates will be calculated as the number of received valid forms over the number of expected forms. Differences between groups in compliance will be tested by use of Fisher's exact test at every time point.

We will use descriptive statistics to describe how patients rate symptom severity and interference with function at each time point. Error bar graphs for each of the symptoms will be constructed at each time point. The proportion of patients rating their symptoms to be 7 or

greater (on a 0-10 scale) will also be reported. We will construct individual patient profiles for each of the selected symptoms to describe the individual patients' patterns of change over time. We will calculate the mean core symptom severity, mean severity of the MDASI-BT or MDASI-SP and mean symptom interference at the time of clinical evaluation. Estimates of differences in the mean symptom severity and mean symptom interference between responders and non-responders will be estimated in the intent to treat population. All patients with at least one valid questionnaire, BT and/or SP, will be included in the analyses. Questionnaires completed at study registration will be considered baseline. All questionnaire data received after randomization will be used in the primary analyses.

Differences of at least 2 points will be classified as the minimum clinically meaningful change in the symptom severity and symptom interference measures. For example, an increase of 2 points or more would mean a moderate improvement, whereas a decrease of 2 points or more would be interpreted as moderate worsening. For individual symptoms, a rise in a symptom score means deterioration, whereas a reduced score means improvement of the specific symptom.

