#### **1.1.2.5 Patient Related Outcome Objectives:**

- To evaluate longitudinal changes in symptom measures and determine the impact of the therapy on these parameters.
- To measure symptom burden over the course of therapy to evaluate differences between patients individual symptom severity, overall mean symptom severity, and difference in scores on the interference items between responders and nonresponders.
- To describe the variability of symptom severity longitudinally over the treatment course and follow-up period.

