- In addition, any subject who develops clinical signs and symptoms of cardiac failure should undergo an LVEF assessment and ECG.

3.7.8 After enrollment on the clinical trial, patients will complete as baseline measures the MDASI-BT or MDASI-SP. The patient will continue to complete the MDASI-BT and/or MDASI-SP at the time of clinical evaluation with MRI as long as the clinical therapy is being administered, unless clinical deterioration makes self-report not possible before that time. The time when patients are unable to complete the self report questionnaires will be used as part of the study analysis. The MDASI-BT and/or MDASI-SP will be completed only by the patient, unless changes in vision or weakness make this difficult. If this occurs, then the caregiver or research assistant may read the questions to the patient or assist with marking the severity number or score as described by the patient. A patient caregiver may complete the questionnaires as a patient-preference proxy if the patient’s deficits preclude self report.

3.7.9 Off treatment follow-up will continue on the following schedule until the patient meets off study criteria.

3.7.9.1 For patients with stable disease or response, MRI surveillance should continue every 2 months for 1 year after treatment completion, then every 3 months for 1 year, then every 4 months for 1 year, then every 6 months until progressive disease is noted, death or lost to follow-up.

3.7.9.2 Patients removed from study treatment for disease progression or treatment-related toxicity should continue to be followed with quarterly (every 3 month) updates of treatment regimens, disease status and survival.

3.7.9.3 Stable disease (SD) patients who develops progression while being followed on the “off treatment follow-up schedule”, will continue with follow-up requirements on the PD off treatment follow-up schedule, until patient meets off study criteria.

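### The MDASI comparison of responders with non-responders uses neither the baseline score nor a landmark and is at risk of bias; the off-treatment form schedule needs reconciling

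*Combined protocol and SAP*

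**What the plan says.** **Objectives.** Section 1.1.2.5 sets three symptom objectives. The second asks how severity and interference differ between responders and non-responders. The third asks for the variability of severity "longitudinally over the treatment course and follow-up period".

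**Analysis.** In the MDASI-BT part of Section 8, differences in mean severity and mean interference "between responders and non-responders will be estimated in the intent to treat population". On who is included: "All patients with at least one valid questionnaire, BT and/or SP, will be included in the analyses". On baseline: "Questionnaires completed at study registration will be considered baseline". The planned look at change within patients is descriptive: "We will construct individual patient profiles for each of the selected symptoms". On relevance: "Differences of at least 2 points will be classified as the minimum clinically meaningful change". On size: "The sample size for this trial was based on the primary end point of the study". The responder sentence gives no covariate, change score, visit, landmark or missing-data method. The same text assigns data received after randomization to the primary analyses, although the trial has one arm, so it is unclear whether baseline scores enter.

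**Collection.** Section 3.7.8 has forms completed at MRI evaluations "as long as the clinical therapy is being administered, unless clinical deterioration makes self-report not possible before that time", and Section 3.7.4 sets the same limit. The study calendar (Section 3.6) has MDASI every 8 weeks in courses 3-24. It also has an MDASI mark, with no footnote or interval, in the column for discontinuation, completion and post-protocol therapy. Section 3.7.8 allows a caregiver proxy and says that the time at which self-report becomes impossible will enter the analysis, without saying how.

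**The concern.** Responders and non-responders are not assigned groups. A patient becomes a responder only by staying on treatment until a scan shows a response. Progression is a reason to stop therapy (Section 3.8.1), and stopping therapy ends the forms described in Sections 3.7.4 and 3.7.8. Three things can then separate the group means even if response has no effect on symptoms:

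- **Baseline confounding:** patients with fewer symptoms at entry may be more likely to respond.
- **Guarantee time:** responders must have lasted on therapy long enough to be scored as such.
- **Informative dropout:** forms end close to deterioration, and sooner in non-responders. Section 3.4.2 adds an opposite mechanism, since patients with response or clinical benefit may stop at 12 months.

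The intent-to-treat label does not help, because response was not allocated. At stake is the answer to the second symptom objective. The third is affected by the unclear off-treatment collection. The primary endpoint is not touched.

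**Working it through.** The plan gives no power or precision for MDASI, so there is no figure to reproduce.

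**1. How fast on-therapy collection thins out.** Take the 10.5-month median from Section 8, an exponential time, and the assumption that progression ends therapy. The fraction progressed is 1 - 2^(-t/10.5), with t in months:

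| Week | t | Progressed |
|---|---|---|
| 8 | 1.84 | 11% |
| 16 | 3.68 | 22% |
| 24 | 5.52 | 31% |
| 48 | 11.04 | 52% |

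These are progression fractions, not a measure of bias. Earlier forms stay in the analysis, and the calendar plans a form at discontinuation.

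**2. Precision.** The half-width of a 95% interval is 1.96 x SD x sqrt(1/nR + 1/nN). Inputs: 50 patients (Section 8) and 20% responders, which is the benchmark in Section 1.2.2 used as an assumption. This gives 10 against 40, with sqrt(1/10 + 1/40) = 0.354. The documents give no SD; 1.5 to 2.5 points is assumed.

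- SD 1.5: 1.04 points
- SD 2.0: 1.39 points
- SD 2.5: 1.73 points

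Over response rates of 10-30% and these SDs the range is 0.91 to 2.31.

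**3. Illustrative simulation with no true effect of response.** Assumptions, none from the documents except the 10.5-month median, the 14-month scenario and the 7-month scenario in Section 8:

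- exponential time on therapy and a form every 8 weeks on therapy;
- between-patient SD 1.5, residual SD 1;
- response first seen at the week 8, 16 or 24 scan if still on therapy, giving 22-27% responders;
- where stated below, a one-SD worse baseline shortens time on therapy by the factor exp(-0.3) = 0.74, response propensity correlates 0.3 with milder baseline symptoms, and severity rises 2 points in the last 2 months on therapy.

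Responder minus non-responder difference in points (negative means responders look better), at the 10.5-month median:

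| Setting | Unadjusted | Change from baseline, no landmark | Change from baseline, week-24 landmark |
|---|---|---|---|
| No links, no late rise | -0.01 | 0.00 | 0.00 |
| Late rise only | -0.20 | -0.20 | 0.00 |
| Baseline linked to time on therapy | -0.06 | 0.00 | 0.01 |
| Baseline linked to time and response | -0.75 | 0.00 | 0.01 |
| Both links and late rise | -1.00 | -0.25 | -0.03 |

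Over medians of 7 to 14 months the last row runs from -0.97 to -1.07 unadjusted, -0.21 to -0.31 for change alone, and -0.03 to -0.05 at the landmark. Responders supplied about 6 to 8.5 forms each and non-responders about 4 to 6.5; 9-17% of patients had no post-baseline form.

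Baseline accounts for most of the larger differences. Guarantee time combined with a late rise accounts for the part that change scores alone do not remove. The landmark column is a favourable case: baseline was taken without measurement error, and response did not affect time on therapy after the landmark.

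**4. Off-treatment forms.** Sections 3.7.4 and 3.7.8 yield none. The calendar yields at least one, at discontinuation. Section 3.7.9.1 schedules 12/2 + 12/3 + 12/4 = 6 + 4 + 3 = 13 surveillance MRIs over three years, but only for patients with stable disease or response.

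**The case against.** The strongest reply is that this is a descriptive secondary estimate. The objective asks how the groups differ, not what response causes; no test on the scores is planned; and the text is silent on method rather than committed to a poor one. Baseline is defined and individual profiles of change are planned. The simulated spurious difference can be zero, and at its largest is about half the 2-point threshold (1.07/2 = 0.54). Proxy completion and the recorded time of inability to self-report soften the dropout.

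Much of this limits the point without removing it. A descriptive difference is still read as a symptom contrast. Elsewhere, Section 8 specifies change from baseline for laboratory values, vital signs and weight, but not here. Neither the proxy rule nor the unspecified use of time to inability repairs the comparison. A difference of 1.07 is also about as large as the 1.04 half-width at an SD of 1.5.

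Three stronger readings are tempting and are not supported:

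- **That nothing is collected after therapy, so the follow-up objective cannot be met.** The calendar marks MDASI at discontinuation and post-protocol therapy, and patients on post-protocol lapatinib have visits every 2 months. The text and the calendar conflict; what is missing is a stated repeat interval.
- **That groups are compared visit by visit, so late visits set responders against surviving stable patients only.** The wording about each time point belongs to the descriptive summaries and the compliance test. The responder sentence names no time.
- **That the estimate is biased by a known amount.** The inputs needed to size the bias are not in the documents.

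**Conclusion.** The concern holds as a risk of bias in one secondary estimate. The plan compares groups defined after baseline, on forms tied to time on therapy, without the collected baseline score and without a landmark. A better method is available from data already collected.

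The size is uncertain: 0 to -1.07 points in the illustrative settings. It is zero if baseline severity is unrelated to response and time on therapy and symptoms do not rise before therapy ends. The documents give no ground for assuming those conditions. Change from baseline without a landmark left up to -0.31, so both parts of the correction matter.

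On the third objective, the follow-up period is poorly supported rather than impossible to describe: Sections 3.7.4 and 3.7.8 disagree with the calendar, and no repeated off-treatment schedule is stated.

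**What to change.** **Analysis.** Estimate the responder difference in mean severity and mean interference with a linear mixed model that has the baseline score as covariate. Fix response status at a stated landmark scan, for example the one before cycle 5, and compare only later scores. State the missing-data assumption, since dropout after the landmark remains. Keep the all-patient descriptive summaries alongside.

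**Collection and objective.** Reconcile Sections 3.7.4 and 3.7.8 with the calendar on whether and when forms are due off treatment. Limit the third symptom objective to the period in which forms are actually collected. Adding MDASI at the Section 3.7.9.1 MRI visits would not repair the loss of progressing patients: those visits cover stable or responding patients, while patients removed for progression have quarterly status updates under Section 3.7.9.2. Accrual is also closed (Section 2.3), so follow-up already missed cannot be recovered.

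**Cost.** The changes are to wording and need no new data. The downside is that patients who progress before the landmark drop out of that one comparison. With a scan at week 16 and the 10.5-month exponential, that is about 22%, or 0.22 x 50 = 11 of 50 patients. Responses first seen after the landmark would count as non-response in it.

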## **9 HUMAN SUBJECTS PROTECTIONS**

### **9.1 RATIONALE FOR SUBJECT SELECTION**

This study was designed to include women and minorities, but was not designed to measure differences of intervention effects. Males and females will be recruited with no preference to gender. No exclusion to this study will be based on race. Minorities will actively be recruited to participate. Ependymomas occur in patients of all races and although there is a slight predominance in men, this is a disease that is also common in women. The molecular targets of the Temozolomide and Lapatinib within the tumor are not known to be different among patients based on gender or race; hence this study will be open to all adults.

### **9.2 PARTICIPATION OF CHILDREN**

Individuals under the age of 18 will not be eligible to participate in this study because of unknown toxicities of the study agents in the pediatric patient. Furthermore, the targets of the Temozolomide and Lapatinib are not as prevalent in pediatric malignant ependymomas and therefore, the efficacy of this regimen will be initially determined in the adult population before consideration of its use in pediatrics.

### **9.3 EVALUATION OF BENEFITS AND RISKS/DISCOMFORTS**

The primary risk to patients participating in this research study is from the toxicity of Temozolomide and Lapatinib, or both drugs. Both are investigational agents in the treatment of ependymoma. The protocol provides for detailed and careful monitoring of all patients to assess for toxicity. Toxicity data from the current dose level will be collected and reviewed to ensure that there were no severe toxicities that would preclude further patient enrollment. Patients will be treated with therapeutic intent and response to the therapy will be closely monitored.

## **9.4 RISKS/BENEFITS ANALYSIS**

### **9.4.1 Benefits**

The potential benefit to a patient on this study is a reduction in the bulk of their tumor and improvement in cancer lesions, which may or may not have favorable impact on symptoms and/or survival.

### **9.4.2 Risks**

Risks include the possible occurrence of any of a range of side effects which are listed in the Consent Document or this protocol document. Frequent monitoring for adverse effects will help to minimize the risks associated with administration of the study agents.

### **9.4.3 Risks/Benefits Analysis**

The potential benefits from this therapy are disease stabilization or shrinkage and a reduction in symptoms caused by the brain tumor such as neurological deficits and headache. Given the efforts to minimize risk with the administration of this combination, this protocol involves greater than minimal risk, but presents the potential for direct benefit to individual subjects.

## **9.5 CONSENT AND ASSENT PROCESS AND DOCUMENTATION**

All patients who are being considered for this trial will undergo informed consent prior to being enrolled on the trial. The PI or associate investigator will perform the consenting process. Patients and family members when applicable will be asked to read the consent and will be encouraged to ask questions. It will be stated clearly that participation in the research study is voluntary and that participants can withdraw from the study without losing benefits they would otherwise be entitled to. Patients will be enrolled after the consent document has been signed. Separate consents will be obtained for any surgical procedures performed. The informed consent process will be documented in the patient's medical record and on the informed consent document. This process will be performed by the local Principal Investigator or designee.

If new safety information results in significant changes in the risk/ benefit assessment, the consent form will be reviewed and updated as necessary. All subjects (including those already being treated) will be informed of the new information, be given a copy of the revised form, and be asked give their consent to continue in the study.

## **10 PHARMACEUTICAL INFORMATION**

There will be no IND obtained for the use of lapatinib in this study.

This study meets the criteria for exemption for an IND as this investigation is not intended to support a new indication for use or any other significant change to the labeling; the drugs are already approved and marketed and the investigation is not intended to support a significant change in advertising; and the investigation does not involve a route of administration or dosage level in use in a patient population or other factor that significantly increases the risks (or decreases the acceptability of the risks) associated with the use of the drug product.

### **10.1 TEMOZOLOMIDE AGENT INFORMATION (TEMODAR)**

Please refer to the package insert for comprehensive information.

#### 10.1.1 Formulation

10.1.2 Other Names: - methazolastone; Temozolomide is supplied in white opaque, preservative-free, two-piece, hard gelatin capsules of the following p.o. dosage strengths: 5 mg, 20 mg, 100 mg, 180 mg and 250 mg. Each capsule contains drug substance in combination with lactose, anhydrous NF, colloidal silicon dioxide NF, sodium starch glycolate NF, tartaric acid NF, and stearic acid NF. The capsule shells contain gelatin NF, titanium dioxide USP, and sodium lautyl sulfate NF.

10.1.3 Mode of Action: Alkylating agent of imidazotetrazinone class.

#### 10.1.4 Storage and Stability

The capsules are packaged in 30 cc, 28 mm, 48 Type I amber glass bottles (30 capsules/bottle) and should be stored at 25°C but temperatures between 15 and 30 degrees centigrade are permissible. Capsules are stable for at least 30 months when stored in amber glass bottles at this temperature.

10.1.5 Supply: Commercially available

#### 10.1.6 Pharmacokinetics

Temozolomide is rapidly and completely absorbed after oral administration; peak plasma concentrations occur in 1 hour. Food reduces the rate and extent of temozolomide absorption. Mean peak plasma concentration and AUC decreased by 32% and 9%, respectively, and  $T_{max}$  increased 2-fold (from 1.1 to 2.25 hours) when temozolomide was administered after a modified high-fat breakfast. Temozolomide is rapidly eliminated with a mean elimination half-life of 1.8 hours and exhibits linear kinetics over the therapeutic dosing range. Temozolomide has a mean apparent volume of distribution of 0.4 L/kg (%CV=13%). It is weakly bound to human plasma proteins; the mean percent bound of drug-related total radioactivity is 15%.

#### 10.1.7 Metabolism and Elimination

Temozolomide is spontaneously hydrolyzed at physiologic pH to the active species, 3-methyl-(triazen-1-yl)imidazole-4-carboxamide (MTIC) and to temozolomide acid metabolite. MTIC is further hydrolyzed to 5-amino-imidazole-4-carboxamide (AIC), which is known to be an intermediate in purine and nucleic acid biosynthesis and to methylhydrazine, which is believed to be the active alkylating species. Cytochrome P450 enzymes play only a minor role in the metabolism of temozolomide and MTIC. Relative to the AUC of temozolomide, the exposure to MTIC and AIC is 2.4% and 23%, respectively. About 38% of the administered temozolomide total radioactive dose is recovered over 7 days; 37.7% in urine and 0.8% in feces. The majority of the recovery of radioactivity in urine is as unchanged temozolomide (5.6%), AIC (12%), temozolomide acid metabolite (2.3%), and unidentified polar metabolites(s) (17%). Overall clearance of temozolomide is about 5.5 L/hr/m^2.

#### 10.1.8 Special Populations

**10.1.8.1 Creatinine Clearance:** Population pharmacokinetic analysis indicates that creatinine clearance over the range of 36-130 mL/min/m^2 has no effect on the clearance of temozolomide after oral administration. The pharmacokinetics of temozolomide have not been studied in patients with severely impaired renal function ( $CL_{cr} < 36$  mL/min/m^2). Caution should be exercised when temozolomide is administered to

patients with severe renal impairment. Temozolomide has not been studied in patients on dialysis.

**10.1.8.2 Hepatically Impaired Patients:** In a pharmacokinetic study, the pharmacokinetics of temozolomide in patients with mild to moderate hepatic impairment (Child's-Pugh Class I-II) were similar to those observed in patients with normal hepatic function. Caution should be exercised when temozolomide is administered to patients with severe hepatic impairment.

**10.1.8.3 Gender:** Population pharmacokinetic analysis indicates that women have an approximately 5% lower clearance (adjusted for body surface area) for temozolomide than men. Women have higher incidences of grade 4 neutropenia and thrombocytopenia in the first cycle of therapy than men.

**10.1.8.4 Population pharmacokinetic analysis indicates that age (range 19-78 years) has no influence on the pharmacokinetics of temozolomide.** In the anaplastic astrocytoma study population, patients 70 years of age or older had a higher incidence of grade 4 neutropenia and grade 4 thrombocytopenia in the first cycle of therapy than patients under 70 years of age. In the entire safety database, however, there did not appear to be a higher incidence in patients 70 years of age or older.

**10.1.8.5 Drug-Drug Interactions:** In a multiple dose study, administration of temozolomide with ranitidine did not change the  $C_{max}$  or AUC values for temozolomide or MTIC. Population analysis indicates that administration of valproic acid decreases the clearance of temozolomide by about 5%. The clinical implication of this effect is not known. Population analysis failed to demonstrate any influence of co-administered dexamethasone, prochlorperazine, phenytoin, carbamazepine, ondansetron,  $H_2$ -receptor antagonists, or phenobarbital on the clearance of orally administered temozolomide.

